**LIST OF ABBREVIATIONS**

Ab	Antibody
AASLD	American Association for the Study of Liver Diseases
ACTG	AIDS Clinical Trials Group
AE	Adverse Event/Adverse Experience
AIDS	Acquired Immune Deficiency Syndrome
ALT	Alanine Aminotransferase
APRI	AST to Platelet Ratio Index
ASI	Addiction Severity Index
AST	Aspartate Aminotransferase
AUDIT	Alcohol Use Disorders Identification Test
CHC	Community Health Center
CBO	Community-Based Organization
CD4	Cluster of Differentiation 4
CDC	Centers for Disease Control and Prevention
CI	Confidence Interval
CITI	Collaborative Institutional Training Initiative
CFR	Code of Federal Regulations
Co-I	Co-Investigator
CRC	Clinical Research Center
CRF	Case Report Form
CT	Computed Tomography
DAA	Direct-acting Antiviral Agent
DOH	Department of Health
DOT	Directly Observed Therapy
DSM	Data and Safety Monitoring
EASL	European Association for the Study of the Liver
eCRF	Electronic Case Report Form
eDOT	Electronic Directly Observed Therapy
EDTA	Ethylenediaminetetraacetic Acid
ETR	End of Treatment Response
FDA	Food and Drug Administration, DHHS
FDC	Fixed Dose Combination
FIB	Fibrosis
FQHC	Federally Qualified Health Center
FWA	Federalwide Assurance
GAD	Generalized Anxiety Disorder
GCP	Good Clinical Practice
HAART	Highly Active Anti-Retroviral Therapy

HBsAg	Hepatitis B Surface Antigen
HBV	Hepatitis B Virus
HCC	Hepatocellular Carcinoma
HCV	Hepatitis C Virus
HERO	Hepatitis C Real Options
HgB	Hemoglobin
HIPAA	Health Insurance Portability and Accountability Act
HIV	Human Immunodeficiency Virus
HRC	Human Rights Campaign
HU	Harvard University
ICF	Informed Consent Form
ICH	International Conference on Harmonisation
ID	Identification
IDSA	Infectious Diseases Society of America
IEC	Independent or Institutional Ethics Committee
IFN	Interferon
IMB	Information-Motivation-Behavioral
INHSU	International Network of Hepatitis in Substance Users
IOM	Institute of Medicine
IRB	Institutional Review Board
IU	International Units
JHU	The Johns Hopkins University
LSAB	Local Stakeholder Advisory Board
MARS	Medication Assisted Recovery Services
mDOT	Modified Directly Observed Therapy
mg	Milligram
mL	Milliliter
MMC	Montefiore Medical Center
MOP	Manual of Procedures
MRI	Magnetic Resonance Imaging
MSM	Men who have Sex with Men
N	Number (Typically Refers to Subjects)
NAMA	National Alliance for Medication Assisted Recovery
NATAP	National AIDS Treatment Advocacy Project
NIH	National Institutes of Health, DHHS
NSAB	National Stakeholder Advisory Board
NVHR	National Viral Hepatitis Roundtable
NYCDOH	New York City Department of Health
NYCDOHMH	New York City Department of Health and Mental Hygiene
OAT	Opiate Agonist Treatment

[figure not shown]
OHRP	Office for Human Research Protections
OR	Odds Ratio
OTP	Opioid Treatment Program
PCORI	Patient-Centered Outcomes Research Institute
PD	Protocol Deviation
PHQ	Patient Health Questionnaire
PI	Principal Investigator
PN	Patient Navigator
POC	Point of Care
PWID	People Who Inject Drugs
PY	Person-Years
RA	Research Assistant
RAV	Resistance-associated Variant
RCT	Randomized Control Trial
REDCap	Research Electronic Data Capture
RNA	Ribonucleic Acid
SAE	Serious Adverse Event/Serious Adverse Experience
SAS	Statistical Analysis System
SD	Standard Deviation
SDCC	Statistical and Data Coordinating Center
SMS	Short Message Service
SOP	Standard Operating Procedure
SVR	Sustained Virologic Response
TAG	The Advocacy Group
TAU	Treatment as Usual
UCSF	University of California San Francisco
UNM HSC	University of New Mexico Health Science Center
URI	University of Rhode Island
US	United States
UT	Urine Toxicology
UW	University of Washington
VAS	Visual Analogue Scale
VL	Viral Load
WHO	World Health Organization
WVU	West Virginia University

**Figure 1: Schematic of Study Design**

## PROTOCOL SUMMARY

Title:	Patient-Centered Models of HCV Care for People Who Inject Drugs
Design:	Two arm study evaluating modified directly observed therapy (mDOT) versus patient navigator (PN) to deliver HCV treatment to PWID in two health settings: (1) opioid treatment program (OTP), (2) community health center (CHC) -Sites in eight cities (16 programs)
	Total number of subjects: Up to 1000 subjects will be enrolled and randomized with an expected 600 participants initiating treatment.
	Participants: 600 subjects on treatment Arm A: (1) OTP, N=150; (2) CHC, N=150 Arm B: (1) OTP, N=150; (2) CHC, N=150
Population:	Adults of any gender with current Hepatitis C Virus (HCV) infection, people with recent active injection drug use, 18 – 70 years old.
Number of Sites:	Eight Sites (Montefiore Medical Center, New York; West Virginia University, Morgantown; University of Washington, Seattle; University of Rhode Island, Providence; University of California San Francisco; The Johns Hopkins University, Baltimore; University of New Mexico, Albuquerque)
Study Duration:	Approximately 6 years
Subject Participation Duration:	Up to 180 weeks: up to 12 weeks of pre-treatment evaluation, 12 weeks of treatment, 12 weeks of follow-up to determine Sustained Virologic Response (SVR) 12, and 144 weeks of follow-up to determine long-term SVR and reinfection
Description of Intervention:	Participants will be randomized to one of two treatment

model arms: A: mDOT or B: PN, at one of two clinical sites: 1) opioid treatment program (OTP) or (2) community health center (CHC) setting.

Objectives:

1. To determine whether SVR-12 rates are higher among those randomized to mDOT compared to those randomized to PN, among People Who Inject Drugs (PWID) treated at opioid treatment program (OTP) and community health centers (CHC).
2. We will also examine the following outcomes overall, and by randomization arm (mDOT vs. PN):
  - (1) HCV treatment initiation
  - (2) Adherence
  - (3) Treatment completion
  - (4) Drug resistance
  - (5) HCV reinfection
3. To examine factors associated with key study outcomes (treatment initiation, adherence, SVR, drug resistance and HCV reinfection) using quantitative and qualitative methods.

Estimated Date of Completion:

2022

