## 5.4 Randomization

Up to 1000 patients will be recruited, with patients randomized to PN or mDOT in a 1:1 ratio (500 subjects in each group) in variable block sizes of 2-6 via central, computer-generated randomization provided by the UNM Statistical and Data Coordinating Center (SDCC). Randomization will occur in blocks to ensure comparison groups of approximately equal size. Given that the intervention will not be blinded, block size will vary to prevent anticipation of treatment arm assignment.

Two special randomization strategies (stratification and blocking) will be used to avert imbalances in prognostic factors or treatment settings, and to ensure comparison groups of approximately equal size. Participants will be stratified by 3 factors: city, OTP vs. community health center and stage of liver disease (cirrhosis v. no cirrhosis).

In addition, adaptive re-weighting of random allocation in a pseudo urn randomization fashion will be made when N~300 has been enrolled to balance the sample size between mDOT and PN arms. Specifically, as we hypothesize that number of randomized subjects who will initiate treatment will be larger in the PN arm, unbalancing between arms is likely to occur during the course of the study. Of note, therefore, a randomized subject will not necessarily be a clinical treatment subject but will be included in the comparison of treatment initiation.

To adjust for this potential unbalance, we will adjust randomization based on observed allocation ratio at the middle of trial if the overall allocation difference is greater than 5% (i.e., <47.5% vs. 52.5%).

Storage and dispensing of random allocation codes will be made in a centralized fashion. The UNM SDCC will generate and store the codes for all sites and types of clinics, and will be embedded into the Research and Electronic Data Capture (REDCap) data management system in the backend so that the identification of a treatment assignment will be ready and immediate without contacting the coordinating center when requested through the REDCap electronic request form by a responsible research staff at the sites whenever a new eligible participant is enrolled. The UNM SDCC will also be responsible for conducting re-weighted randomization, if necessary, at the middle of the trial.

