### 11.3 Study Hypotheses

**SVR:** Among subjects who initiate HCV treatment, rate of SVR will be higher in the mDOT vs. PN arm. We hypothesize that SVR rate will be 80% in PN arm.

**Treatment initiation rate:** A higher proportion of patients in the PN arm will initiate treatment compared to the mDOT arm, which is expected to have 60% treatment initiation rate.

**Adherence rate:** Patients in the mDOT arm will have higher adherence rate, compared to the PN arm which is expected to have 80% adherence rate.

**Treatment completion rate:** Patients in the mDOT arm will have higher treatment completion rate, compared to the PN arm, which is expected to have 80% completion rate.

**Detectable resistance:** Patients in the PN arm will have higher resistance rate, compared to the mDOT arm. We hypothesize that the majority (65%) of patients who fail to achieve SVR will develop detectable resistance, yielding an overall 10% resistance rate.

**Reinfection rate:** The hypothesis is that there will be a minimum 5% reinfection rate based on meta-analysis of reinfection rates in patients treated with IFN-based regimens.

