## 11.4 Sample Size Determination

Sample size N=300 per arm, or a total of N=600, was determined based on feasibility of recruitment from all sites during the study period. Power analysis for each hypothesis below is conservatively conducted based on a reduced sample size (N= 270 per arm, or N=540 in total) after considering 10% attrition rates. The target power is 80% with a two-sided significance level of 0.05. To this end, minimally detectable effect sizes and widths of 95% confidence intervals were computed with those parameters and the sample size after attrition.

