### 5.5 Power analysis

The HERO study was planned to recruit N=300 participants in each arm in the mITT sample. Considering the base 80% SVR rate in the PN arm, a minimum difference of 9% between the two arms will be detected (i.e., 89% vs. 80%, OR=2.1) with the planned sample size in a multivariable logistic regression model in which adjusting variables explain 10% of variation in the predictor variable. This study posits that a >9% difference in SVR between the PN and DOT groups will be clinically significant based on studies that showed that SVR in treatment naive patients was >90%.

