#### 8.2.2 Power analysis

We hypothesize that a higher proportion of patients in the PN arm will initiate treatment compared to the DOT arm, which is expected to have 60% treatment initiation rate. With the planned N=1000 ITT sample size, we will be able to detect a minimum of 12% difference (i.e., 60% vs. 72%, OR=0.58) in any outcome in a multivariable logistic regression model in which confounding variables will explain 10% of variation in the predictor variable.

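### The SAP gives power for the planned 1000 randomised and 300 initiators per arm although its Table 1 is headed 754, and the detectable initiation differences of 7 and 12 points are wrong even at 1000

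*Protocol*

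**What the plan says.** The protocol summary plans as follows: "Up to 1000 subjects will be enrolled and randomized with an expected 600 participants initiating treatment". Section 5.4 has "patients randomized to PN or mDOT in a 1:1 ratio (500 subjects in each group"). Section 11.4 adds "Sample size N=300 per arm, or a total of N=600, was determined based on feasibility of recruitment", and computes power on a reduced size ("N= 270 per arm, or N=540 in total) after considering 10% attrition rates"), with 80% power at two-sided 0.05.

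On initiation, protocol 11.3 expects a higher proportion in PN "compared to the mDOT arm, which is expected to have 60% treatment initiation rate". It gives no expected PN rate. Protocol 11.10 says that 60% versus 67% is detectable with all 1000 randomised. SAP 8.2.2 says of the same comparison: "With the planned N=1000 ITT sample size, we will be able to detect a minimum of 12% difference", that is, 60% versus 72%. Both assume that covariates explain 10% of the variation in the arm indicator.

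On SVR, SAP 5.5 says "The HERO study was planned to recruit N=300 participants in each arm in the mITT sample" and gives 9 points (89% versus 80%) as the detectable difference. It also treats a difference above 9 points as clinically significant. SAP 6.3 works from 600 in the mITT sample.

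SAP Table 1 (section 4.1) heads its columns DOT N=375 and PN N=379. It does not say which analytic sample these are. No power statement in the SAP uses 754.

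**The concern.** Two things look wrong.

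First, the SAP carries a tabulated size and a set of power statements that do not refer to each other. If 754 is the number randomised, 60% initiation in DOT gives 375 × 0.60 = 225 initiators, not 300. The 9-point SVR figure is the primary power claim and also the plan's threshold for a clinically significant difference, so readers may use it to judge what a null result excludes.

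Second, the two documents give different minimum detectable initiation differences, 7 and 12 points, for the same N, base rate and covariate assumption. At most one can be right. Initiation is the outcome on which PN is expected to do better, so its stated sensitivity matters.

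**Working it through.** **Inputs.** SVR 80% (PN) versus 89% (DOT); two-sided 0.05; target power 80%; covariate R² = 0.10 (protocol 11.4 and 11.10, SAP 5.5). DOT initiation 60% (protocol 11.3, SAP 8.2.2). Table 1: 375 and 379. PN initiation of 67% or 72% is an assumption, taken from the plan's detectable-difference illustrations.

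**Formula.** Pooled two-proportion test with effective sizes m = 0.9 × n:

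power = Φ{ [ |p₁ − p₂| − 1.96 √( p̄(1 − p̄)(1/m₁ + 1/m₂) ) ] / √( p₁(1 − p₁)/m₁ + p₂(1 − p₂)/m₂ ) }

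where p̄ is the size-weighted mean. The detectable difference is the one at which power equals 80%.

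**Step 1: reproduce the SVR figure.** At 300 per arm, m = 270: (0.09 − 1.96 × 0.03115) / 0.03091 = 0.937, so power is 82.6% and the detectable difference is 8.7 points. At the protocol's 270 per arm, power is 78.4% and the difference 9.2 points. The stated 9 points reproduces.

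**Step 2: initiators from 754.** DOT: 375 × 0.60 = 225. PN: 379 × 0.67 = 254, or 379 × 0.72 = 273. Totals: 479 or 498. Reaching 600 would need 600/754 = 79.6% initiation.

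**Step 3: SVR power at those sizes.** For 225 and 254, m = 202.5 and 228.6: (0.09 − 1.96 × 0.03517) / 0.03440 = 0.612, so power is 73.0%.

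| Initiators (DOT / PN) | Power, 89% v 80% | Detectable difference |
|---|---|---|
| 300 / 300 (SAP 5.5) | 82.6% | 8.7 points |
| 225 / 254 (60% / 67% of 754) | 73.0% | 9.7 points |
| 225 / 273 (60% / 72% of 754) | 74.2% | 9.6 points |
| 75% of 754 in both arms | 80.3% | 9.0 points |
| 80% of 754 in both arms | 82.7% | 8.7 points |
| 375 / 379 (if Table 1 shows initiators) | 90% | 7.9 points |

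The break-even point: 80% power needs 253 per arm unadjusted, or 253/0.9 = 281 with R² = 0.10. From 754 that is 2 × 281/754 = about 75% initiation, or 2 × 253/754 = about 67% with no covariate adjustment.

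**Step 4: initiation, 60% base.**

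- N=1000, 67%: m = 450 per arm, (0.07 − 1.96 × 0.03210) / 0.03201 = 0.222, so power is 58.8%, or 63.3% with no covariate adjustment. Reaching 80% needs 742 per arm unadjusted, or 742/0.9 = 825 adjusted.
- N=1000, 72%: (0.12 − 1.96 × 0.03158) / 0.03133 = 1.855, power 96.8%.
- N=540, 72%: m = 243, (0.12 − 1.96 × 0.04298) / 0.04263 = 0.839, power 79.9%. The 12 points therefore matches the protocol's post-attrition initiator count, not 1000.
- Detectable difference with R² = 0.10: 8.9 points at N=1000 and 10.2 at N=754.

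**The case against.** The case against has real force on SVR.

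- The protocol's 1000 is a ceiling, and the SAP calls its sizes planned. Leaving prospective power at the planned size is common practice. This stands: 754 is a shortfall not carried into the power sections, not a contradiction.
- Table 1 is an unfilled shell, its list of characteristics is marked as still to be determined, and its sample is unlabelled. If the 754 are initiators, SVR power is 90%. This stands as a condition. The randomised reading is more plausible because the table is meant to describe the study participants, SAP 4.2 uses baseline comparisons to verify randomisation, and the arms are near-equal, as blocking would give.
- The PN rates of 67% and 72% are detectable values, not forecasts, and observed initiation is not in the documents. This stands; they serve only as an assumed range.
- At the stated odds ratio of 2.1 (89.4% versus 80%; 89% gives 2.02), power with 479 to 498 initiators is 77% to 78% adjusted and 81% to 82% unadjusted. The shortfall is modest on any reading.
- A null result would be read mainly from the adjusted odds ratio and its interval, which SAP 5.4 reports. That limits the harm.

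Three stronger readings are tempting and are not supported.

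A reader might infer that 600 initiators from 1000 randomised, being 60% in both arms, conflicts with a higher PN rate and so costs power. It does not. At 67% or 72% in PN, 1000 randomised gives 300 DOT plus 335 or 360 PN initiators, and SVR power of 84% to 86%.

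A reader might therefore want 300 per arm replaced by unequal targets. Protocol 5.4 foresees more PN initiators and aims at balanced arms: "adaptive re-weighting of random allocation in a pseudo urn randomization fashion will be made when N~300 has been enrolled".

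A reader might also deduct the protocol's 10% attrition from the SAP's sizes. SAP 5.3.1 counts undetermined SVR as failure in the primary mITT analysis, so no participant is lost there.

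None of these objections touches the initiation figures, which fail at the full planned 1000.

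**Conclusion.** The point holds in two parts of different strength.

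The initiation figures are wrong as stated, whatever Table 1 means. From a 60% base with R² = 0.10, the minimum detectable difference is about 8.9 points at N=1000. The protocol's 7 points has 59% to 63% power there. The SAP's 12 points has 97% power, so it is achieved but is not a minimum; at 754 it still has at least 91%. The 754 causes neither error.

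The SVR part is conditional. If 754 is the randomised number, DOT initiation is 60% and PN initiation is 67% to 72%, the 9-point claim has about 73% to 74% power instead of at least 80%, and the detectable difference is 9.6 to 9.7 points. At about 75% overall initiation, or if the 754 are initiators, there is no shortfall. The documents do not settle which case applies, and the SAP should.

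**What to change.** Wording changes only; no added enrolment and no change to the analysis.

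1. State in SAP Table 1 which analytic sample the 375 and 379 describe.
2. In protocol 11.10 and SAP 8.2.2, replace 7 and 12 points with one figure: from a 60% base with R² = 0.10, about 9 points at N=1000 and about 10 points at N=754. Correct the example percentages and odds ratios to match.
3. In SAP 5.5, keep the planned 300 per arm as the design basis. If Table 1 is the randomised sample, add the detectable SVR difference for 754 over a stated initiation range: about 9 points at 75% to 80%, and 9.7 points at 60% in DOT and 67% in PN.
4. Carry the same range into SAP 6.3, whose subgroup figures start from 600.

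The cost is a few sentences and, if initiation is near 60%, a slightly less favourable statement of SVR power.

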## 2 Background Information and Scientific Rationale

### 2.1 Background Information

#### HCV epidemic in people who inject drugs (PWID)

PWID have the highest incidence and prevalence of HCV in the U.S. and globally [1]. In the U.S. an estimated 43% of current or former PWID aged 40-65 years have chronic HCV [2]. Prevalence of HCV varies by age and duration of injecting, but meta-analyses show that in developed countries, including the U.S., mean cumulative incidence was over 20%, and prevalence was 72% in PWID with a history of 10 year of injecting [2]. The Centers for Disease Control and Prevention (CDC) estimates at least 30,000 new HCV infections per year [3], predominantly among PWID, with a 44% increase in the number of acute cases from 2010 to 2011 [4]. This increase has been associated with an expanding PWID population, especially in non-urban areas across the U.S. [5], and has been related in part to increases in prescription opioids, followed by related transitions to injection drug use [6, 7]. Addressing methods to optimize access to curative HCV treatment in PWID is a priority given their role in the growing HCV epidemic in the U.S. HCV causes up to 15,000 deaths annually, and is the leading cause of liver transplantation in the U.S. [8-10]. Treatment effectiveness among PWID is crucial because PWID remain the leading risk group for HCV infection [11]. PWID have the highest prevalence and incidence of HCV in the U.S., yet HCV treatment is rarely provided to PWID. In two systematic reviews of interferon-based treatment for PWIDs, overall SVR was 56%, and response rates were comparable to large RCTs [12, 13]. International guidelines from the American Association for the Study of Liver Diseases (AASLD)/ Infectious Diseases Society of America (IDSA), European Association for the Study of the Liver (EASL), International Network of Hepatitis in Substance Users (INHSU), and the World Health Organization (WHO) all recommend treatment for HCV infection among PWID [14-17]. With significant scale up of HCV treatment of PWID, overall HCV prevalence could be reduced by up to 75% within 15 years [18]. Nevertheless, few data exist on direct-acting antiviral agents (DAAs) treatment outcomes in PWID, and therefore PWID are often not eligible to receive DAAs.

[figure not shown]
#### HCV treatment uptake among PWIDs is limited by multiple barriers

Hepatitis C treatment uptake among PWID has been limited by multiple interrelated barriers at the level of the patient, the provider and the system (Figure 2) [19, 20]. Patient-level barriers included poor knowledge related to HCV and treatment as well as the absence of symptoms, which often results in a low perceived need for treatment. These issues are compounded by general barriers to health care access (e.g., having insurance, a primary care provider), competing comorbidities, which may require more

immediate attention as well as factors which impede stability including unemployment, unstable housing, lack of transportation, incarceration and ongoing substance use [21-25]. Providers are often unwilling to prescribe HCV treatment to even former PWID because of concerns related to ongoing substance use, low adherence and the potential risk of reinfection [20, 25].

Some studies have suggested that physicians have suboptimal knowledge regarding HCV and its treatment which can impact which patients get tested, referred and who initiate treatment [20, 26]. A major structural barrier is the cost of the medications and the associated monitoring. But beyond cost, additional structural barriers include insufficient locations where HCV testing can be performed and where treatment can be delivered [20, 27]. There is also a dearth of providers who can treat HCV and patient navigators dedicated to spearheading HCV-infected PWID and others through treatment. Finally, HCV care has historically been delivered in specialist settings which means it is segregated from other services that PWID utilize including primary care, opiate substitution and HIV care.

**Figure 2: Barriers to Treatment**

### **Efficacy of new HCV regimens for HCV-infected patients**

New direct-acting antiviral agents (DAAs) are efficacious in >95% of treatment-naïve patients [14]. The interferon-free DAA fixed dose combination of ledipasvir 90 mg and sofosbuvir 400 mg once daily for 12 weeks is associated with SVR rates of >95% in genotype-1 infected patients [14], and is associated with fewer side effects than previous regimens: fatigue 13% - 18%, headache 11% - 17%, and nausea 6% - 9%. The interferon-free DAA fixed-dose regimen of sofosbuvir 400 mg once-daily (nucleotide polymerase) and velpatasvir 100 mg once-daily (NS5A inhibitor) has demonstrated high efficacy (95-96% SVR12) with a treatment duration of 12 weeks in treatment-naïve patients with HCV genotypes 1-6 [28], and was approved for use by the Food and Drug Administration (FDA) on June 28, 2016. The availability of a simplified IFN-free DAA-based once-daily regimen of sofosbuvir/velpatasvir may further enhance the capacity to scale-up HCV treatment among PWID. A pan-genotypic regimen can help increase access for PWID by eliminating the need for genotypic testing prior to treatment. Therefore, fixed-dose sofosbuvir/velpatasvir will now be used for this study.

